5.1.4 Primary Endpoints Assessed during Primary Follow-up

The two primary endpoints for the ATP cohort analyses are:

1. Time from 14 days post-Dose 3 to molecular detection of the first new malaria infection through to 12 months post-Dose 3
2. Number of new molecularly confirmed malaria infections during the same follow-up period used for ATP primary endpoint 1

The two primary endpoints for the TVC analyses are:

1. Time from first vaccination to molecular detection of the first new malaria infection through to the Month 20 study visit post first vaccination
2. Number of new molecularly confirmed malaria infections during the same follow-up period used for TVC primary endpoint 1

For the measurement of new malaria infection detection endpoints in the ATP cohort, “through to xx months post-Dose 3” (e.g., xx=12 months) means through to the Month yy study visit (e.g., if xx=12, then yy=14 for Groups 1-4 and yy=19 for Group 5). This approach rather than measurement of exactly xx months post-Dose 3 (irrespective of visit date) is used to ensure that follow-up for all study arms only includes time periods before Dose 4, which is administered at the Month 14 study visit for Groups 3 and 4 and at the Month 20 study visit for Groups 2 and 5. If the Month yy visit is missed, the time-to-event is right-censored at the last parasite negative sample collection date prior to the missed Month yy visit.

For analyses of the TVC, for both primary endpoints, new molecularly confirmed malaria infections are counted after the first vaccination through to the Month 20 visit, for all study arms and all comparisons. Infections detected in any sample collected on the day of enrollment (whether from the enrollment visit or an unscheduled visit completed on the day of enrollment) are excluded, i.e., not treated as new infections for either primary endpoint because, in these samples, we cannot rule out a persistent infection acquired prior to enrollment.

For analyses of the ATP cohort, for both primary endpoints, the comparator group (rabies control vaccination) window of follow-up for capturing outcomes differs depending on the vaccine group to which it is compared. In particular, the primary objectives in the ATP cohort study primary endpoints occurring after 14 days post-Dose 3 through to the visit scheduled 12 months post-Dose 3 (Month 14 for Groups 2, 3, 4 and Month 19 for Group 5), such that the follow-up period for registering events is Month 2.5-14 for each of Groups 2, 3, 4 vs. Control and is Month 7.5-19 for Group 5 vs. Control (the first row of Table 1 describes all of these follow-up periods).

For comparing the vaccine study groups head-to-head, all pairwise comparisons for the TVC analyses use a follow-up period starting from first vaccination through to the Month 20 study visit, as for the analyses of each RTS,S/AS01E vaccine arm vs. control. The ATP cohort analyses for these pairwise study group comparisons use a follow-up period of 11.5 months starting at 14 days post-Dose 3 (Table 1).

Table 1. Follow-up Intervals (in Months) Since First Vaccination for Counting New Malaria Infections for the Primary Analyses in the ATP Cohort (Each Entry is for the Comparison of Two Study Arms, where 2.5 indicates 14 days post Dose 3 in Groups 1-4, 7.5 indicates 14 days post Dose 3 in Group 5, 14 indicates the Month 14 study visit, and 19 indicates the Month 19 Study Visit)*

	GP2 R012-20**	GP3 R012-14**	GP4 Fx012-14	GP5 Fx017
GP1 Cont.	2.5-14 vs. 2.5-14		2.5-14 vs. 2.5-14	7.5-19 vs. 7.5-19
GP2 R012-20			2.5-14 vs. 2.5-14	2.5-14 vs. 7.5-19
GP3 R012-14				2.5-14 vs. 7.5-19
GP4 Fx012-14				2.5-14 vs. 7.5-19

*“Study visit” refers to a monthly longitudinal sampling visit through Month 20.

**GP2 and GP3 are pooled for comparison with GP1 over 2.5-14 months given GP2 and GP3 are identical during this follow-up period. Similarly, GP2 and GP3 are pooled for comparison with GP4 during 2.5-14 months and are pooled for comparison with GP5 (2.5-14 months for GP2 and GP3 vs. 7.5-19 months for GP5).

Table 2 lists the set of primary vaccine efficacy and relative vaccine efficacy analyses that are done, with follow-up periods, and grouping the analyses into three sets (vs. control, vs. the standard R012-20 vaccine regimen, and head-to-head novel vaccine regimens).

Table 2. Study Groups Compared to Assess Vaccine Efficacy or Relative Vaccine Efficacy Based on New Malaria Infection Endpoint Data Through Month 20 (Primary Endpoints)

Analysis Type (Cohort)	Study Group and Follow-up Comparison
Assess Vaccine Efficacy (TVC)	GP2 M0-20 vs. GP1 M0-20
	GP3 M0-20 vs. GP1 M0-20
	GP4 M0-20 vs. GP1 M0-20
	GP5 M0-20 vs. GP1 M0-20
Assess Vaccine Efficacy (ATP)	GP2 + GP3 pooled M2.5-14 vs. GP1 M2.5-14

	GP4 M2.5-14 vs. GP1 M2.5-14 or T2
	GP5 M7.5-19 vs. GP1 M7.5-19
Assess Relative Vaccine Efficacy vs. Standard regimen R012-20 (TVC)	GP3 M0-20 vs. GP2 M0-20 GP4 M0-20 vs. GP2 M0-20 GP5 M0-20 vs. GP2 M0-20
Assess Relative Vaccine Efficacy vs. Standard regimen R012-20 (ATP)	GP4 M2.5-14 vs. GP2 + GP3 pooled M2.5-14 GP5 M7.5-19 vs. GP2 + GP3 pooled M2.5-14*
Assess Relative Vaccine Efficacy (Other Comparisons) (TVC)	GP4 M0-20 vs. GP3 M0-20 GP5 M0-20 vs. GP3 M0-20 GP5 M0-20 vs. GP4 M0-20
Assess Relative Vaccine Efficacy (Other Comparisons) (ATP)	GP5 M7.5-19* vs. GP4 M2.5-14

*Because different 11.5-month intervals are compared, the control group GP1 is used in the analysis to correct for potential bias due to secular trends (e.g., caused by seasonality); Section 7.5 provides details on the analysis.

5.1.5 Primary Endpoints Assessed over Shorter-term Follow-up

The primary endpoints are also analyzed only counting new malaria infections through 14 months post first vaccination (TVC analyses) or through 7 months post Dose 3 (ATP analyses), when immunity may be greatest and hence protection putatively greater. The short-term endpoints are specified for the ATP cohort as:

1. Time from 14 days post-Dose 3 to molecular detection of the first new malaria infection through to 7 months post-Dose 3
2. Number of new molecularly confirmed malaria infections during the same follow-up period specified immediately above

Similarly, the short-term endpoints are specified for the TVC as:

1. Time from first vaccination to molecular detection of the first new malaria infection through to the Month 14 study visit after first vaccination
2. Number of new molecularly confirmed malaria infections during the same follow-up period specified immediately above

Table 3 shows the group comparisons and time periods of follow-up for analysis of the primary outcomes over shorter term follow-up.

Table 3. Study Groups Compared to Assess Vaccine Efficacy or Relative Vaccine Efficacy Based on New Malaria Infection Endpoint Data Through Month 14 (Analyses of the Primary Endpoints Shorter Term)

Analysis Type	Study Group and Follow-up Comparison
Assess Vaccine Efficacy (TVC)	GP2 + GP3 pooled M0-14 vs. GP1 M0-14
	GP4 M0-14 vs. GP1 M0-14
	GP5 M0-14 vs. GP1 M0-14
Assess Vaccine Efficacy (ATP)	GP2 + GP3 pooled M2.5-9 vs. GP1 M2.5-9
	GP4 M2.5-9 vs. GP1 M2.5-9
	GP5 M7.5-14 vs. GP1 M7.5-14
Assess Relative Vaccine Efficacy vs. Standard regimen R012 (TVC)	GP4 M0-14 vs. GP2 + GP3 pooled M0-14
	GP5 M0-14 vs. GP2 + GP3 pooled M0-14
Assess Relative Vaccine Efficacy vs. Standard regimen R012(ATP)	GP4 M2.5-9 vs. GP2 + GP3 pooled M2.5-9
	GP5 M7.5-14 vs. GP2 + GP3 pooled M2.5-9*
Assess Relative Vaccine Efficacy (Other Comparisons) (TVC)	GP5 M0-14 vs. GP4 M0-14
Assess Relative Vaccine Efficacy (Other Comparisons) (ATP)	GP5 M7.5-14* vs. GP4 M2.5-9

*Similar to Table 2, because different 6.5-month intervals are compared, the control group GP1 is used in the analysis to correct for potential bias due to secular trends (e.g., caused by seasonality); Section 7.5 provides details on the analysis.

5.1.6 Primary Endpoints Assessed over Longer-term Follow-up through Month 32

Longitudinal samples taken at Month 23, 26, 29, 32 are subjected to haplotyping in the same way as monthly samples drawn at monthly visits before and including Month 20.

To assess durability of VE, the primary endpoints are also analyzed (i) counting new molecularly confirmed malaria infections in the TVC cohort through 32 months after the first vaccination, and (ii) counting new molecularly confirmed malaria infections in the ATP cohort through 24 months post-Dose 3. Note that membership in the ATP cohort does not depend on whether Dose 4 is received.

The two primary endpoints assessed for durability for the ATP cohort analyses are:

1. Time from 14 days post-Dose 3 to molecular detection of the first new malaria infection through to 24 months after Dose 3
2. Number of new molecularly confirmed malaria infections during the same follow-up period used for the endpoint defined immediately above

The two primary endpoints assessed for durability for the TVC analyses are:

1. Time from first vaccination to molecular detection of the first new malaria infection through to the Month 32 study visit after first vaccination
2. Number of new molecularly confirmed malaria infections during the same follow-up period used for the endpoint specified immediately above

Table 4 summarizes the group comparisons and time periods for including new malaria infections using data through Month 32. Note that there is no scheduled Month 31 visit. Therefore, ATP cohort analyses listed in Table 4 that involve Group 5 will include new malaria infections detected in this group in the time period between 14 days post-Dose 3 and no later than the minimum of exactly 24 months post-Dose 3 and the time of completion of the Month 32 visit.

Table 4. Study Groups Compared to Assess Vaccine Efficacy or Relative Vaccine Efficacy Based on New Malaria Infection Endpoint Data Through Month 32 (Analysis of Primary Endpoints Longer Term)

Analysis Type	Study Group and Follow-up Comparison
Assess Vaccine Efficacy (TVC)	GP2 M0-32 vs. GP1 M0-32
	GP3 M0-32 vs. GP1 M0-32
	GP4 M0-32 vs. GP1 M0-32
	GP5 M0-32 vs. GP1 M0-32
Assess Vaccine Efficacy (ATP)	GP2 M2.5-26 vs. GP1 M2.5-26
	GP3 M2.5-26 vs. GP1 M2.5-26
	GP4 M2.5-26 vs. GP1 M2.5-26
	GP5 M7.5-31 vs. GP1 M7.5-31
Assess Relative Vaccine Efficacy vs. Standard regimen R012-20 (TVC)	GP3 M0-32 vs. GP2 M0-32
	GP4 M0-32 vs. GP2 M0-32
	GP5 M0-32 vs. GP2 M0-32
Assess Relative Vaccine Efficacy vs. Standard regimen R012-20 (ATP)	GP3 M2.5-26 vs. GP2 M2.5-26
	GP4 M2.5-26 vs. GP2 M2.5-26
	GP5 M7.5-31 vs. GP2 M2.5-26*
Assess Relative Vaccine Efficacy (Other Comparisons) (TVC)	GP4 M0-32 vs. GP3 M0-32
	GP5 M0-32 vs. GP3 M0-32
	GP5 M0-32 vs. GP4 M0-32
Assess Relative Vaccine Efficacy (Other Comparisons) (ATP)	GP4 M2.5-26 vs. GP3 M2.5-26
	GP5 M7.5-31 vs. GP3 M2.5-26*
	GP5 M7.5-31 vs. GP4 M2.5-26*

*Similar to Tables 2 and 3, because different 23.5-month intervals are compared, the control group GP1 is used in the analysis to correct for potential bias due to secular trends (e.g., caused by seasonality); Section 7.5 provides details on the analysis.

5.2 Two Tiers of Sample Evaluation

This subsection summarizes the dried blood spot samples that are drawn and subjected to genotyping/haplotyping, providing the amplicon data needed to define occurrence of new malaria infections; the section STUDY ENDPOINTS describes periods of follow-up for counting new malaria infections for analyses of vaccine efficacy and relative vaccine efficacy. The following sequential approach is used for sample evaluation to investigate the study objectives, with Tier 1 sampling essential to addressing the Primary Objective, and Tier 2 sampling used for exploratory analyses, where Tier 1 sample evaluation is performed after the primary immunization series (Doses 1, 2, 3) and Tier 2 sampling performed after the booster immunization series, respectively. Two sets of samples will be analyzed:

1. Tier 1: All dried blood spot samples collected monthly from all subjects during the first 20 months (expect approximately 31,500 samples) and all clinical malaria cases during the first 20 months (expect approximately 14,400 samples) from all treatment arms of the study.
2. Tier 2: All dried blood spot samples collected quarterly after the first 20 months for one year following the first booster RTS,S dose (expect approximately 9,000 samples) and clinical malaria cases after the first 20 months through Month 32 (expect approximately 8,640 samples) from all treatment arms of the study.

6 VARIABLES OF INTEREST

6.1 Independent Variable

The primary covariate of interest is treatment assignment.

6.2 Candidate Adjustment Variables

Some of the statistical analyses described in the STATISTICAL ANALYSIS section make use of baseline and post-baseline participant-level variables that may be prognostic for subsequent new malaria infection. In particular, the following baseline variables are accounted for in development of a “baseline risk score” variable that is predictive of the rate of new malaria infection and in covariate-adjusted analyses such as conducted by targeted maximum likelihood estimation:

1. Study site

2. Age
3. Sex

In addition, the set of post-baseline time-dependent variables that may be prognostic for malaria infection and may be accounted for in some statistical analyses are:

1. mol[FOI]
2. Rainfall (typically the strongest prognostic factor)

The mol[FOI] by a follow-up time t is defined as the number of new infections molecularly detected between enrollment and time t . For comparisons involving differential calendar periods (e.g., comparisons of Group 5 with any of Groups 2–4 in the ATP cohort), we may use monthly rainfall (in mm), separately for each site, spanning the calendar time during which participants were followed, as reported at <http://worldweatheronline.com>. Other information accompanying the history of previous malaria infections (timing of infections and clinical malaria cases, parasitemia, dates of malaria infection or clinical malaria, use of antimalarial treatments, and relevant clinical characteristics) may be utilized as available.

Antimalarial treatment is a time-dependent variable of special interest and has the potential to bias estimates of certain target parameters of interest, as described below in subsection 7.1.

7 STATISTICAL ANALYSIS FOR PRIMARY OBJECTIVES

7.1 Structure of the Analysis Approach for Assessing Vaccine Efficacy and Relative Vaccine Efficacy

We first consider the following three issues that require attention across the primary and exploratory objectives:

1. Hierarchy of analyses and false-positive control/multiplicity adjustment
2. Adjustment for baseline covariates
3. Antimalarial treatment

For issue 1, as structured in Tables 2, 3, 4, the three sets of comparison types are (1) comparisons of active vaccine study groups vs. rabies control; (2) comparisons of novel active vaccine study groups vs. the standard RTS,S/AS01E regimen; and (3) comparisons of novel active vaccine study groups. Comparisons of Group 4 vs. Group 1 and of Group 5 vs. Group 1 are of primary interest and will not be adjusted for multiplicity in either cohort or for any time period of follow-up.

For all remaining comparisons, the multiplicity adjustment approach for primary objective analyses is as follows: For comparisons of type (1) (remaining comparisons minus the two primary ones), (2) and (3) separately, for each cohort (ATP and TVC) and time-period of follow-up separately, q -values controlling the false discovery rate

(calculated using the *p.adjust* function in R) and Holm-adjusted p-values controlling the familywise type 1 error rate will be computed along with unadjusted p-values for the set of multiple comparisons. Results are expected to be correlated across cohorts and follow-up periods, such that full FWER adjustment is deemed overly stringent on type I error control at the expense of reduced power.

For issue 2, methods based on targeted maximum likelihood will use Super Learner as an intermediate step, both for predicting the probability of a missing measurement of primary endpoint 2 and for predicting the value of primary endpoint 2, allowing the entire set of pre-specified baseline covariates to potentially be used in predictions (see Section 7.6.1 for definition of an observed/known primary endpoint 2). In contrast, methods not using targeted maximum likelihood (e.g., Cox proportional hazards models) will instead stratify by study site in the study site-pooled analysis and possibly adjust for the “ATP Propensity Score” univariate baseline covariate defined below in Section 7.5 if this propensity score is found to be sufficiently predictive of the outcome under study.

For issue 3, the primary analyses will disregard antimalarial treatment because new malaria infections are observed in the trial within an arbitrary window following drug treatment onset. Nonetheless, because antimalarial treatment may still reduce the risk of a new infection for some time period after treatment onset and because the administration of treatment may be less frequent in vaccine arms if there is protective efficacy, there remains a potential for bias due to differential amount of post-treatment follow-up time characterized by a reduced risk of new infection across study groups. Therefore, we will also conduct a sensitivity analysis in which the primary analyses will be repeated after removing from the follow-up time the period of 14 days following the onset of each antimalarial treatment.

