4.2 Primary Objective

The primary objective of MAL-095 is to estimate and compare vaccine efficacy (VE) against new molecularly confirmed malaria infection(s) across parasite genotypes among the vaccine arms of the trial, using amplicon sequencing and genotyping to detect new infections (see Section 5.1.3 for the definition of a new infection). Infections will be detected by molecular methods from monthly samples or samples collected at unscheduled visits for clinical assessment.

Throughout, vaccine efficacy refers to a comparison of a study endpoint between an active RTS,S vaccine regimen (one of Groups 2 through 5) vs. the rabies control arm, and relative vaccine efficacy refers to a comparison of a study endpoint between two active RTS,S vaccine regimens (among Groups 2 through 5). Vaccine efficacy and relative vaccine efficacy are assessed based on two types of outcomes:

(Primary endpoint 1) first new molecularly confirmed *P. falciparum* infection detection over a specified follow-up period;

(Primary endpoint 2) all new molecularly confirmed *P. falciparum* infection detections accumulated over a specified follow-up period.

As stated in the MAL-095 protocol, vaccine efficacy and relative vaccine efficacy against each primary outcome type will be assessed in analyses of both the ATP and TVC cohorts, as co-primary objectives.

The follow-up periods for assessing the two outcome types in the primary and exploratory analyses, for each of the ATP and TVC cohort analyses, are specified in Section 5.

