5.1.1.1 Modified Definition of Molecular Parasite Positivity for Month 32 Analyses

During inspection of sequencing data in support of the M20 interim analysis, a post hoc decision was made to revise the minimum read count for calling a haplotype as present in a sample from 50 to 325 sequencing reads. The 50 read threshold established during formulation of the original SAP v1.0 was chosen to optimize precision and recall using a truth set of sequencing data from mock samples. However, upon analysis of the much larger M20 trial dataset, it was determined that a revised threshold of 325 reads would more effectively reduce signals of false positive haplotype calls due to sporadic transfer of DNA among samples within sequencing batches housed in the same multi-well plate.

5.1.2 Definition of Primary Endpoint 1

We define the time to primary endpoint 1 variable as the number of days from the time origin in each analysis to the visit date associated with the first molecular detection of a new malaria infection, irrespective of

- the number of missed scheduled visits preceding this event,
- whether this event occurred within a certain time interval following the onset of antimalarial treatment, and/or
- an earlier occurrence of secondary-case clinical malaria (with no molecular detection).

For participants with no molecular detection of a new infection at any visit within a considered follow-up period, their time to primary endpoint 1 will be right-censored at the collection date of the last parasite negative sample within the follow-up period in each analysis.

5.1.3 Definition of Primary Endpoint 2

For a participant with no missed scheduled visits and no missed samples from attended visits, we estimate the total number of new molecularly confirmed malaria infections in a given follow-up period as the number of occurrences of molecular detection of a new malaria infection during this period regardless of

- whether any such detection occurred within a certain time interval following the onset of antimalarial treatment, and/or
- any occurrence(s) of secondary-case clinical malaria.

For a participant with missed scheduled visits or missed samples from attended visits, the definition of an observed/known primary endpoint 2 in a given follow-up period accounts for missing sequence data, and the definition is stated in Section 7.6.1.

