Vaccine efficacy against primary endpoint 2 for a given vaccine arm vs. the control arm will be assessed by the additive difference in the mean number of new molecularly confirmed malaria infections in each vaccine arm vs. the mean number of new molecularly confirmed malaria infections in the control vaccine arm. The targeted maximum likelihood estimator of Porter et al. (2011) will be used, which incorporates information in baseline study characteristics predictive of whether data are missing or predictive of the number of new molecularly confirmed malaria infections. This method also provides a way to estimate the variance of the estimated mean number of new molecularly confirmed malaria infections in each study arm. Based on these variance estimates, Wald tests will be used to test for the additive difference VE differing from zero and to obtain a 95% CI. These analyses are done for each comparison specified in Tables 2–4 with the control group as the comparison arm.

Similarly, the same methods will be used to test for differences in the mean numbers of new molecularly confirmed malaria infections between vaccine arms, and to compute 95% CI for these differences. Again Wald 95% CIs and Wald 2-sided p-values are used. These analyses are done for each comparison specified in Tables 2–4.

7.6.1 Handling of Loss to Follow-up and Missing Visit Data for Primary Endpoint 2

The number of new molecularly confirmed malaria infections must be estimated based on the genotyping/haplotyping data, and we use an operational definition for what data availability constitutes enough information for the study endpoint to be considered observed/known for an individual. A participant's endpoint is considered to be observed/known if both (a) s/he had at least one visit with genotyping data in the 75-day period leading up to the last scheduled visit in the given follow-up period (e.g., Month 0 to 20, Month 2.5 to 14, Month 7.5 to 19), and (b) s/he had genotyping data from at least 50% of scheduled visits during the given follow-up period. If the last scheduled visit in the given follow-up period was missed, then the 75-day period is keyed off of the target date of the missed visit. The premise for this estimator is that, with these available data, it will be possible to accurately estimate the number of new molecularly confirmed malaria infections during the follow-up period.

TMLE inference about reverse cumulative distribution functions (RCDFs)

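### For endpoint 2, the 14-day antimalarial sensitivity analysis removes time from an analysis that uses no person-time, so against control it tends to shrink the difference instead of correcting it

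*SAP*

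**What the plan says.** SAP Section 7.1, issue 3, sets antimalarial treatment aside in the primary analyses, on the ground that "new malaria infections are observed in the trial within an arbitrary window following drug treatment onset". It then allows that "the administration of treatment may be less frequent in vaccine arms if there is protective efficacy", which leaves a potential for bias from a "differential amount of post-treatment follow-up time characterized by a reduced risk of new infection across study groups". The response is a sensitivity analysis that repeats the primary analyses after "removing from the follow-up time the period of 14 days following the onset of each antimalarial treatment". No separate rule is given for endpoint 2.

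Endpoint 2 is one of those primary analyses. SAP Section 4.2 defines it as "all new molecularly confirmed *P. falciparum* infection detections accumulated over a specified follow-up period", and Section 5.1.3 makes it a per-child tally: "we estimate the total number of new molecularly confirmed malaria infections in a given follow-up period as the number of occurrences of molecular detection". Section 7.6 compares arms by the "additive difference in the mean number of new molecularly confirmed malaria infections in each vaccine arm" against control, estimated by TMLE, with no offset, rate or exposure term. Under Section 7.6.1 a count is treated as known if the child has genotyping data within 75 days of the last scheduled visit and "s/he had genotyping data from at least 50% of scheduled visits during the given follow-up period". A known count is not rescaled for time observed.

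Protocol Section 6.1 also planned a negative binomial regression for endpoint 2 with an offset for follow-up. SAP Section 7.6 does not contain that model, and the SAP's modification history does not mention dropping it.

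**The concern.** If control children are treated more often, they spend more time at drug-reduced risk. Their infection count is then too low and the control-minus-vaccine difference is understated. A useful check should move the estimate toward a larger difference, or show that it does not move.

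In a Cox model, removing the days takes both events and time at risk out of the likelihood, so the check can work. In a difference of mean counts there is no time to take out. All the removal can do directly is discard infections detected in those days, and a more heavily treated control arm loses more of them. A smaller difference could then be misread as a sign that treatment had inflated the primary result. The documents plan no other check on this bias for the primary objective. The treatment covariate in SAP Section 9.4 serves post-hoc effect-modification models.

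**Working it through.** The plan gives no figure for this analysis, so there is none to reproduce. The check compares expected counts under the two ways of handling the removed days.

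**Inputs from the documents**
- ATP follow-up is 11.5 months (SAP Section 5.1.4), taken as T = 350/365.25 = 0.958 years.
- The window is 14 days (SAP Section 7.1), so w = 14/365.25 = 0.0383 years.
- Low treatment rates: 0.5 per year in control and 0.29 in the standard schedule. These are planning incidences of clinical malaria in protocol Section 6.2, used as a stand-in for treatments.
- High treatment rate: 14,400 expected clinical samples (SAP Section 5.2) / (1,500 children × 20/12 years) = 5.76 per child-year. This counts samples, not treatments, and averages over all arms. Assigning it to control is only an upper scenario.

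**Assumptions**
- Control infection rate L = 4 per year, with a true rate reduction of 30% (vaccine 2.8).
- Relative risk inside the window ρ = 0.5, with the drug effect confined to 14 days and no overlap of windows.
- In the two higher scenarios, vaccine-arm treatment is 0.7 times control.

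**Formulas**, with n treatments per child over T:
- Primary count = L × (T − w·n·(1 − ρ))
- Count after removal = L × (T − w·n)
- Person-time version = L × (T − w·n)/(T − w·n) = L, scaled back to T

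The removal therefore lowers the control-minus-vaccine difference by ρ·w·(L_c·n_c − L_v·n_v). This is zero only if ρ = 0 (no detections in the windows). It is positive when control has more infections, at least as many treatments and some detections in the windows.

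**Worked row**, 0.5 versus 0.29 per year: n_c = 0.479 and n_v = 0.278.
- Primary: 4 × (0.9582 − 0.0092) − 2.8 × (0.9582 − 0.0053) = 1.128.
- After removal: 4 × (0.9582 − 0.0184) − 2.8 × (0.9582 − 0.0107) = 1.106.

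| Treatments/yr, control vs vaccine | No drug effect | Primary | Count after removal | Person-time | Fall from primary |
|---|---|---|---|---|---|
| 0.5 vs 0.29 | 1.150 | 1.128 | 1.106 | 1.150 | 2% |
| 3 vs 2.1 | 1.150 | 1.038 | 0.925 | 1.150 | 11% |
| 5.76 vs 4.03 | 1.150 | 0.934 | 0.718 | 1.150 | 23% |

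On the relative scale, the first row moves from 29.7% to 29.4% and the last from 27.4% to 24.0%.

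If the drug had no effect (ρ = 1), the primary result would be unbiased at 1.150. Removal would still give 1.106, 0.925 and 0.718, which is a false alarm.

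**20-month horizon.** Assume 10 versus 7 infections, vaccine-arm treatment at 0.29/0.5 = 0.58 times control, and ρ = 0.5. With no drug effect the difference is 3.0. At 0.5 control treatments per year the primary difference is 2.94 and the count after removal 2.89. At 2 per year the figures are 2.77 and 2.54.

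**Simulation.** A day-level simulation (6,000 children per arm) used monthly and treatment-day samples, 4 infections per year, a 40% reduction, about 1.9 versus 1.4 treatments per child, and ρ = 0.5. Differences were:
- no drug effect 1.48; primary 1.41
- count after removal 1.34, or 1.38 when a dropped infection could be re-detected and counted later
- person-time version 1.49

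If the treatment-day sample was removed too, the count difference fell to 0.80 and the person-time version to 0.90.

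**The case against.** The best defence is that the gap is one of implementation. Section 7.1 speaks of follow-up time, which is exposure language, and the protocol's offset model would make the removal meaningful. That stands as far as it goes: the protocol already contains a suitable tool. But the SAP does not carry that model, and the estimator it does specify has no place for the removed days. TMLE does not fill the gap. It handles a count that is wholly missing, and infections per test enter only as an auxiliary predictor.

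A reader might infer that removal can only delete infections, or that it must always worsen the estimate. The documents do not support that. Under the three-sample look-back in SAP Section 5.1.1, an infection dropped in a window can be counted at a later sample. Dropping window samples from the look-back can even create a new infection. In the simulation re-detection roughly halved the shift (1.34 to 1.38, against 1.41) without reversing it.

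A reader might also infer that the SAP declares VE to be biased toward zero. It says only that treatment may be less frequent in vaccine arms and that a potential for bias remains. The direction is an inference, sound for vaccine versus control under that premise. It does not carry over to the head-to-head comparisons in Table 2.

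The size is also open to challenge. Infection rates, the reduction and ρ are assumed, and the 5.76 scenario is loosely sourced. Exact recovery by the person-time version follows from the formula. With monthly sampling it is approximate: in another simulated setting (6 infections per year, about 3.6 versus 2.4 treatments per child) it gave 2.27 against 2.19.

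**Conclusion.** The point holds for endpoint 2 in vaccine-versus-control comparisons. Applied to the SAP's own estimator, the 14-day removal does not correct the bias that Section 7.1 raises. It tends to shrink the difference if control children are treated more often and some new infections are detected in the windows, and it changes nothing if none are. The SAP says the first may occur and that infections are seen after treatment.

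The shift is about 2% of the difference at 0.5 versus 0.29 treatments per year. It is larger at higher rates: about 11% at 3 versus 2.1, and 23% in the upper scenario. These figures rest on the stated assumptions and ignore re-detection, which softens them.

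The documents do not support a reading that the primary endpoint 2 estimate itself is invalidated, because this concerns a sensitivity analysis. The objection does not reach the endpoint 1 Cox analysis. Between vaccine arms the direction is undetermined. The correction is worth making because the check could mislead and the repair is cheap.

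**What to change.** For endpoint 2, run this sensitivity analysis on a rate scale. Count new infections outside the removed days and offset for each child's follow-up minus the removed days, for example with the negative binomial model of protocol Section 6.1. Report the rate ratio and the rate difference.

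State two rules that the SAP leaves open:
- The sample taken on the day of treatment onset is kept. Otherwise the infection that prompted treatment is deleted, and the rate version fails as well.
- Whether samples inside the window still count in the three-sample look-back that defines a new infection.

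The cost is a few lines of SAP text and one extra model on treatment dates that the 14-day rule already requires. The downside is that the result is per unit time and so is not directly the primary difference in counts. Fitting the same rate model with no days removed would give a like-for-like reference.
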